6.1 Potential Risks

Complications associated with standard cardiac catheterization, the use of anesthesia and use of the PASCAL system could lead to reoperation, explant, permanent disability, or death.

The following anticipated adverse events have been identified as possible complications of the PASCAL system and/or implant procedure:

- Abnormal lab values;
- access site AV fistula or pseudoaneurysm;
- allergic reaction to anesthetic, contrast, heparin, Nitinol;
- anemia, may require transfusion
- angina or chest pain
- arrhythmias;
- atrial fibrillation;
- atrial septal defect requiring intervention;
- arterio-venous fistula;
- bleeding;
- cardiac arrest;
- cardiac failure/low cardiac output;
- cardiac injury including perforation, obstruction, or dissection that may require intervention;
- cardiogenic shock;

- chordal entanglement or rupture;
- coagulopathy, coagulation defect or disorder, bleeding diathesis;
- conversion to open valve surgery
- conduction system injury which may require permanent pacemaker implantation
- death;
- deterioration of native valve (leaflet tear/tearing, leaflet retraction, leaflet thickening, or other);
- device deterioration (wear, tear, fracture, calcification, or other);
- device migration (including single leaflet device attachment (SLDA), malposition or embolization requiring intervention;
- device thrombosis requiring intervention;
- emergency cardiac surgery;
- deep venous thrombosis;
- reaction to anti-platelet, anticoagulation agents or contrast media
- dyspnea;
- edema
- electrolyte imbalance;
- emboli/embolization including air, particulate, calcific material, or thrombus;
- endocarditis;
- esophageal irritation;
- esophageal perforation or stenosis;
- exercise intolerance or weakness;
- fever;
- failure to deliver PASCAL to the intended site;
- failure to retrieve any PASCAL system components;
- gastrointestinal bleeding or infarct;
- heart failure;
- heart murmur;
- hematoma;
- hemodynamic compromise;
- hemolysis;
- hemorrhage requiring transfusion or intervention;
- hypertension

- hypotension;
- Implantation of additional transcatheter mitral repair device
- infection;
- Inflammation
- Leaflet damage;
- mesenteric ischemia
- mitral valve stenosis
- mitral valve injury;
- multi-system organ failure;
- myocardial infarction;
- nausea or vomiting;
- nerve injury
- neurological symptoms, including dyskinesia, without diagnosis of TIA or stroke
- non-emergent reoperation;
- nonstructural implant dysfunction;

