7.5 Primary Endpoints

Safety:

Composite of major adverse events (MAE) defined as cardiovascular mortality, stroke, myocardial infarction, new need for renal replacement therapy, severe bleeding and re-intervention for study device related complications at 30 days.

Performance:

- Device success: device is deployed as intended and the delivery system is successfully retrieved as intended at the time of the patient's exit from the cardiac catheterization laboratory. Per device analysis.
- Procedural success: device success with evidence of MR reduction \leq MR2+ at discharge and without the need for a surgical or percutaneous intervention prior to hospital discharge. Per patient analysis.
- Clinical success: procedural success with evidence of MR reduction \leq MR2+ and without MAEs at 30 days. Per patient analysis.

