7.6 Secondary Endpoints and Clinical Outcomes

- Mitral regurgitation reduction at 30 days, 6 months, 1 year and annually thereafter over baseline
- All-cause mortality at 30 days, 6 months, 1 year, and annually thereafter
- Recurrent heart failure hospitalization at 30 days, 6 months, 1 year, and annually thereafter
- Re-intervention rates for mitral regurgitation at 30 days, 6 months, 1 year and annually thereafter
- Composite of major adverse events (MAE) defined as cardiovascular mortality, stroke, myocardial infarction, new need for renal replacement therapy, severe bleeding and re-intervention for study device related complications at 6 months, 1 year and annually thereafter
- Change in Left Ventricular End Diastolic Volume (LVEDV) at 6 months and 1 year and annually thereafter over baseline
- Change in Left Ventricular End Systolic Volume (LVESV) at 6 months and 1 year and annually thereafter over baseline
- Change in Pulmonary Artery Systolic Pressure at 6 months and 1 year and annually thereafter over baseline
- Change in 6MWT distance at 6 months and 1 year over baseline

- Change in Quality of Life (QoL) score, as measured by Kansas City Cardiomyopathy Questionnaire (KCCQ), and EQ5D at 30 days, 6 months and 1 year and annually thereafter over baseline
- Change in NYHA Functional Classification at 6 months and 1 year and annually thereafter over baseline
- Change in BNP/NT-pro-BNP level at 6 months and 1 year and annually thereafter over baseline
- Change in tricuspid regurgitation at 6 months and 1 year and annually thereafter over baseline
- Change in effective regurgitant orifice area (EROA) at 30 days, 6 months, 1 year and annually thereafter over baseline
- Change in mitral regurgitant volume at 30 days, 6 months and 1 year and yearly thereafter over baseline

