Functional/ Secondary Mitral Regurgitation (M-VARC 2015)	Abnormal backflow of blood from left ventricle to left atrium principally caused by global or regional left ventricular remodeling and/or severe left atrial dilation. Severity is as defined by ASE.
Heart Team	Multidisciplinary team consisting of local experts experienced in the care of patients with mitral valve disease. At a minimum, the heart team should include a heart failure/valve cardiologist, an interventional cardiologist skilled in the relevant access and device implantation procedures, a mitral valve cardiac surgeon, and an imaging specialist.
Implant procedure (Index procedure)	The procedure in which placement of the investigational device in the mitral valve regurgitant orifice takes place
Infection	Known infection requiring intravenous antibiotics for other than prophylaxis, and/or extended hospitalization
KCCQ	Kansas City Cardiomyopathy Questionnaire is an instrument used to quantify physical function, symptoms, social function, self-efficacy and knowledge, and quality of life.
Major Adverse Events (MAE)	Cardiac mortality, stroke, myocardial infarction, new need for renal replacement therapy, severe bleeding, and non-elective cardiovascular surgery for device related complications.
Mitral regurgitation	The condition in which incompetency of the mitral valve causes abnormal backflow of blood from the left ventricle to the left atrium during the systolic phase of the cardiac cycle.

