	
 ○ Inotropic agents such as Dobutamine ○ Inodilators such as Milrinone ○ Beta-agonists ○ Vasopressors such as Dopamine, Epinephrine, and Norepinephrine 
Also included would be other invasive or mechanical heart failure treatments such as:
 
 ○ Ultrafiltration ○ CRT (Cardiac Resynchronization Therapy) ○ Hemodynamic assist devices including intra-aortic balloon counterpulsation or left ventricular (LV) or biventricular assist devices 
Treatment with intravenous antiarrhythmic medications or electrical cardioversion and/or ablation in the absence of other intravenous or invasive heart failure treatments would not per se constitute criteria for CHF hospitalization (but would qualify as a cardiovascular hospitalization). Similarly, a CHF exacerbation that can be managed solely by augmentation of oral heart failure therapies does not meet the pre-defined criteria for heart failure hospitalization.
 
Patients hospitalized with heart failure meeting these criteria should further be subclassified into:
 
 ○ Primary (cardiac related) heart failure: this may be due to any cardiac cause, including primary LV dysfunction with or without medication or dietary noncompliance, acute MI, arrhythmias, and worsening valve dysfunction ○ Secondary (non-cardiac related) heart failure: when a non-cardiac primary condition is present such as pneumonia, urinary tract infection, or renal failure, which results in fluid overload or myocardial failure. 
Investigator may need to determine which diagnosis is of prevailing importance (e.g., exacerbation of COPD with bronchospasm and some element of heart failure, or major heart failure exacerbation with secondary bronchospasm). Only primary heart failure should be considered a valid criterion for heart failure hospitalization.

Re-intervention	Any intervention on the previously implanted study device (repair, alteration, or replacement) or study procedure access site post-implant procedure.
Renal Failure	See “Acute Kidney Injury (AKI)”

Renal Replacement Therapy	Treatment that replaces the normal blood-filtering function of the kidneys (e.g. dialysis) due to renal failure (typically Stage 3 AKI)
Serious Adverse Device Event (SADE)	Per ISO 14155:2011: adverse device effect that has resulted in any of the consequences characteristic of a serious adverse event

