#### 6.4. Analyses of Secondary Endpoints

Mitral regurgitation reduction from baseline at 30 days, 6 months, 1 year and annually thereafter will be summarized with counts and percentages.

All-cause mortality rates at 30 days, 6 months, 1 year, and annually thereafter and corresponding 95% confidence intervals will be computed using the Kaplan-Meier algorithm with the standard errors being computed using Greenwood's formula.

Recurrent heart failure hospitalization at 30 days, 6 months, 1 year, and annually thereafter will be analyzed using Poisson regression.

Re-intervention rates for mitral regurgitation at 30 days, 6 months, 1 year and annually thereafter will be summarized with counts and percentages.

Composite of major adverse events (MAE) defined as cardiovascular mortality, stroke, myocardial infarction, new need for renal replacement therapy, severe bleeding and re-intervention for study device related complications at 6 months, 1 year and annually thereafter will be summarized with counts and percentages.

Change from baseline in Left Ventricular End Diastolic Volume (LVEDV), Left Ventricular End Systolic Volume (LVESV), Pulmonary Artery Systolic Pressure, 6MWT distance, BNP/NT-pro-BNP level, effective regurgitant orifice area (EROA) and mitral regurgitant volume at the protocol specified timepoints in the secondary endpoints and clinical outcomes section will be summarized by mean and standard deviation for the PP population. For the analyses of six minute walk test (6MWT), subjects unable to perform the walk due to a medical reason will be considered to have walked an actual distance of zero.

Change from baseline in Quality of Life (QoL) score, as measured by Kansas City Cardiomyopathy Questionnaire (KCCQ), and EQ5D at 30 days, 6 months and 1 year and annually thereafter will be

summarized by mean and standard deviation. Patients that are missing a baseline or follow up values will be excluded from the analysis.

Change from baseline in NYHA Functional Classification at 6 months, 1 year and annually thereafter will be presented as shift from baseline for each of the pre-specified follow-up periods. Subjects that are missing a baseline or follow-up values will be excluded from the paired analysis.

Change from baseline in tricuspid regurgitation at 6 months, 1 year and annually thereafter will be summarized with counts and percentages.

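### As worded, the definition of re-intervention leaves out an additional mitral device placed after discharge beside an untouched implant, so this retreatment enters neither the 30-day MAE composite nor the MR re-intervention rate

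*Protocol*

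**What the plan says.** Protocol Section 17 defines re-intervention by what is worked on: "Any intervention on the previously implanted study device (repair, alteration, or replacement) or study procedure access site post-implant procedure". The entry names neither the mitral valve nor an additional device.

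Two endpoints use the term:
- The primary safety composite (Protocol 7.5, repeated in SAP 3.1 and 6.3) ends with "severe bleeding and re-intervention for study device related complications at 30 days". The later MAE composites in Protocol 7.6 have the same component.
- A secondary endpoint (Protocol 7.6) is "Re-intervention rates for mitral regurgitation at 30 days, 6 months, 1 year and annually thereafter". SAP 6.4 says only how it is tabulated: "Re-intervention rates for mitral regurgitation at 30 days, 6 months, 1 year and annually thereafter will be summarized with counts and percentages". The SAP does not define the term.

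The MAE entry in Protocol Section 17 ends differently: "severe bleeding, and non-elective cardiovascular surgery for device related complications". It does not use the word re-intervention, is limited to surgery, and does not require that the device be touched.

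Protocol 6.1 lists among anticipated adverse events both "device migration (including single leaflet device attachment (SLDA), malposition or embolization requiring intervention" and "Implantation of additional transcatheter mitral repair device".

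Under Protocol 10.1.2 the CEC applies the definitions in the protocol and in its charter. The charter is not among the documents.

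**The concern.** A second device placed beside the first is a foreseeable way to retreat a leaflet repair that has detached or was inadequate. Protocol 6.1 anticipates it. In Protocol 3.4.3.3 the sponsor also quotes the five-year report of a randomised trial of a comparable device, which attributes most early clinical failures to inadequate MR reduction at the index procedure or early single-leaflet attachment.

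The Section 17 definition does not clearly reach this event, because the first implant is not repaired, altered or replaced and the access site is not treated. The mismatch is sharpest for the secondary rate, which is named by its indication (mitral regurgitation) while the definition is tied to a location.

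At stake are the 30-day MAE rate, clinical success (which requires freedom from MAE) and the MR re-intervention rate to five years. For valve retreatments, an omission always favours the device.

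**Working it through.** The plan states no figure on this point. The check is to trace each kind of retreatment through the definitions, read literally.

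| Retreatment | Re-intervention (Section 17)? | MAE under 7.5? | MAE under Section 17? | In MR re-intervention rate? | Clinical success |
|---|---|---|---|---|---|
| A. Additional device beside untouched implant for detachment, after discharge, by day 30 | No | No | No (not surgery) | No | Stands if MR ≤2+ at day 30 and no other MAE |
| B. As A, but before discharge | No | No | No | No | Fails, because procedural success fails |
| C. Non-elective mitral surgery for a device related complication, implant untouched, after discharge, by day 30 | No | No | Yes | No | Depends on which MAE text governs |
| D. As C, but no device was left in place at the attempt | No (no implanted device) | No | Yes | No | Fails, because device success as worded is not met |
| E. Additional device for recurrent MR, no device related complication, after discharge, by day 30 | No | No, by the endpoint's own qualifier | No, same qualifier | No | Stands if MR ≤2+ at day 30 and no other MAE |
| F. Surgery that replaces or alters the implant | Yes | Yes, if for a device related complication | Yes, if also non-elective | Yes, if for MR | Fails if an MAE by day 30 |

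Case A is decisive. Device success is fixed at exit from the catheterization laboratory. The intervention clause in procedural success ends at hospital discharge. Clinical success then needs only MR ≤2+ and no MAE at 30 days. A retreated detachment can therefore be a success on a primary performance endpoint and be absent from both the safety composite and the MR re-intervention rate.

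Case D can arise in the primary analysis, because the per-protocol population (Protocol 9.2, SAP 4) requires only that the device was introduced into the body.

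Size. Inputs are 60 patients in the primary cohort, 30 at the first analysis, and 60 + 50 = 110 pooled (Protocol 7.1 and 9.3). Each uncounted patient with no other MAE moves the MAE rate by:
- 1/60 = 1.7 percentage points
- 1/30 = 3.3 points
- 1/110 = 0.9 points

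Illustration with Clopper-Pearson 95% limits and an assumed starting count of 3: 3/60 = 5.0% (1.0 to 13.9) becomes 4/60 = 6.7% (1.8 to 16.2) with one case added.

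The documents give no retreatment rate, so the chance of at least one uncounted patient, 1 − (1 − q)^n, is shown for assumed rates q:

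| q | n = 60 | n = 110 |
|---|---|---|
| 1% | 45% | 67% |
| 2% | 70% | 89% |
| 3% | 84% | 96.5% |
| 5% | 95% | 99.6% |

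These are crude proportions with the full cohort in the analysis. SAP 6.3 uses Kaplan-Meier for the 30-day composite, which gives the same figure if nobody is censored before day 30.

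**The case against.** The best reply is that the gap is narrow and other parts of the plan cover much of it. Most of that stands.

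- A reader might infer that all retreatments for detachment or recurrent MR escape the primary safety endpoint because of Section 17. The documents do not support this. Section 7.5 counts only "re-intervention for study device related complications at 30 days", so retreatment for MR without such a complication is outside whatever re-intervention means. Non-elective surgery for a device related complication is an MAE under the Section 17 MAE entry.
- A reader might also infer that removing the device is excluded because explant has its own entry. Removal is plausibly an intervention on the device, with the bracketed terms as examples.
- Retreatment before discharge already fails procedural and clinical success.
- SAP 6.6 requires, for FDA device success at 30 days and later, no further procedures related to access or the device. That would catch case A, but only in a supplementary analysis.
- The CEC Charter may define the term more widely, and a second device that stabilises a detached one might be argued to be an alteration. Neither can be checked or settled from the documents, and a primary endpoint component should not rest on either.
- The inclusion of access-site procedures is not a fault in itself. The qualifiers in Sections 7.5 and 7.6 already restrict what enters each endpoint.
- SAP 7.6 tabulates additional and non-study devices, but does not say whether they were placed at the index procedure or later. It is weak evidence that late retreatments are expected.
- The study is single arm and descriptive, with no performance goal, so no stated success decision changes.

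**Conclusion.** The concern holds in a limited form. A percutaneous additional device placed after discharge beside an untouched implant is, on the literal wording, neither a 30-day MAE under either MAE text nor an MR re-intervention, and the patient can still be a clinical success. Mitral surgery that leaves the implant untouched, or that follows an attempt with no device left in place, is also outside the re-intervention definition. If it is non-elective and for a device related complication, its place in MAE turns on the unresolved conflict between Section 7.5 and Section 17. For recurrent MR without a device related complication, the definition affects only the secondary MR rate.

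Each uncounted patient is worth 1.7 points of 60 or 3.3 points of 30. How many there will be is unknown, so it cannot be said that the reported rates will be too favourable, only that any error from this source runs that way. The conclusion rests on a literal reading and on the CEC Charter not widening the term. This is a counting rule that gives a wrong result for an event the protocol foresees, and it should be corrected.

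**What to change.** 1. In Section 17, define re-intervention as any surgical or percutaneous procedure after the index procedure on the mitral valve, the study device or the access site. State that it includes an additional study or non-study mitral device, mitral valve repair or replacement, and device removal.
2. Record the indication for each procedure: device related complication, mitral regurgitation, or access.
3. Count procedures for study device related complications in MAE, and those for mitral regurgitation in the secondary rate.
4. Reconcile the Section 17 MAE entry with Section 7.5, so that a single MAE definition governs.
5. Carry the same text into the SAP (3.1, 3.2, 6.3 and 6.4) and the CEC Charter.

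The cost is wording in the protocol, SAP and charter, and an indication field if the CRF lacks one. Adverse events are already collected throughout follow-up, but any events already adjudicated would need another look. The MAE and re-intervention rates may be slightly less favourable. The change concerns outcome counting only and implies no rule on when a patient should be retreated.

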	
 ○ Stroke ○ Sudden, unexpected death / unknown ○ Tamponade ○ Thromboembolism ○ Other CV cause 
If death was due to a heart failure, it will be sub-classified into:
 
 ○ LV dysfunction ○ RV dysfunction ○ Biventricular dysfunction 
Non-CV Death A diagnosis of non-CV death requires the primary cause to be clearly related to another condition due primarily to an identifiable non-CV cause or etiology. Specific diagnoses may include respiratory failure, pneumonia, trauma, suicide, or any other non-cardiovascular defined causes (e.g., liver disease, malignancies etc.) not included in the previous categories.
 
Primary cause of non-CV death The primary cause of non-CV death will be categorized using the following choices:
 
 ○ Adverse drug reaction or overdose ○ Cancer ○ Gastrointestinal ○ Liver failure ○ Non-cardiovascular infection and sepsis (e.g. pneumonia) ○ Pancreatic ○ Renal failure ○ Respiratory Failure ○ Trauma ○ Other non-CV cause

Degenerative/ Primary Mitral Regurgitation (M-VARC 2015)
	
Abnormal backflow of blood from left ventricle to left atrium due to underlying degenerative/structural mitral valve pathology. Severity is as defined by ASE.

Device success
	
Device is deployed as intended and the delivery system is successfully retrieved as intended at the time of the patient's exit from the cardiac catheterization laboratory. Per device analysis.

Conversion to open mitral valve surgery during a transcatheter
	
Sub-classified as:
 
 ○ Secondary to mitral valve apparatus damage or dysfunction, requiring surgical valve repair or replacement, or

procedure	
 ○ Secondary to procedural complications (such as cardiac perforation, removal of an embolized device, and so on)
Effective Regurgitant Orifice Area (ASE)	Cross-sectional area of the vena contracta of the regurgitant jet
Enrollment	Patient enrollment in this clinical study is established when a patient has signed the informed consent form agreeing to participate in the study and has been deemed eligible for study participation by meeting the study criteria.
Explant	Removal of the study device for any reason.

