### 3. STUDY ENDPOINTS

#### 3.1. Primary Endpoints

##### Safety:

Composite of major adverse events (MAE) defined as cardiovascular mortality, stroke, myocardial infarction, new need for renal replacement therapy, severe bleeding and re-intervention for study device related complications at 30 days.

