## 6.3. Analyses of Primary Endpoints

### Safety:

The primary safety endpoint for this clinical study is a composite of major adverse events (MAE) defined as cardiovascular mortality, stroke, myocardial infarction, new need for renal replacement therapy, severe bleeding and re-intervention for study device related complications at 30 days. The safety endpoints on composite of major adverse events shall be analyzed via the Kaplan-Meier method.

In addition to the safety endpoint analysis, a summary of the percentage of patients who experience an early adverse event ( $\leq 30$  day post-procedure) will be reported for all adverse events. Additionally, linearized rates will be used to summarize adverse events for the late ( $> 30$  days) post-procedure period. The linearized rates will be reported as the number of events occurring after the early post-procedure period per year of patient survival.

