#### 6.6. Additional Analyses per FDA

Per FDA, the success rates based the following definitions will be summarized by counts and percentages.

FDA Device Success (30 day and all post-procedural intervals):

- Alive and stroke free, with
- Original intended device in place, and
- No additional surgical or interventional procedures related to access or the device since completion of the original procedure (i.e., exit from the cath lab/OR), and
- Intended performance of the device:
- Structural performance: No migration, embolization, detachment, fracture, hemolysis, thrombosis or endocarditis, etc., and
- Hemodynamic performance: Maintenance of relief of insufficiency without producing stenosis (stenosis = MV gradient > 5 mmHg; insufficiency = MR >2+), and
- Absence of para-device complications (e.g., leaflet, chordae or papillary muscle damage; LVOT gradient increase > 10 mmHg; hemodynamically significant ASD requiring closure)

FDA Procedural Success (30 day):

- Device success, and
- No device or procedure related SAE's (life threatening bleed; major vascular or cardiac structural complications requiring unplanned reintervention or surgery; stage 2 or 3 AKI (includes new dialysis); MI or need for PCI/CABG; severe HF or hypotension requiring IV inotrope, ultrafiltration or MCS; prolonged intubation > 48 hours)

FDA Technical Success (at exit from OR):

- Alive, with
- Successful access, delivery and retrieval of the device delivery system, and
- Deployment and correct positioning (including repositioning /recapture if needed) of the single intended device, and
- No need for additional unplanned or emergency surgery or re-intervention related to the device or access procedure

FDA Individual Patient Success (1 year):

FDA Device success and all of the following:

- No re-hospitalizations or re-interventions for the underlying condition (e.g., MR, HF)
- Return to prior living arrangement (or equivalent)
- Improvement vs. baseline in symptoms (e.g., NYHA Class improvement > 1 class)
- Improvement vs. baseline in functional status (e.g., 6MWT improvement > 25 meters)
- Improvement vs. baseline in QoL (e.g., KCCQ improvement > 10)

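### The primary safety MAE composite has two conflicting definitions of its device-complication component, and they classify open conversion during the index procedure differently

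*Protocol*

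**What the plan says.** The primary safety endpoint appears in the protocol synopsis, Protocol 7.5, SAP 3.1 and SAP 6.3. In all four the composite ends with "severe bleeding and re-intervention for study device related complications at 30 days". The later MAE endpoints (Protocol 7.6, SAP 3.2 and 6.4) use the same component. The SAP does not define re-intervention; its Definitions section covers only dates and visit windows.

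Four entries in Protocol Section 17 bear on the component:

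- **Re-intervention:** "Any intervention on the previously implanted study device (repair, alteration, or replacement) or study procedure access site post-implant procedure".
- **Major Adverse Events:** "Cardiac mortality, stroke, myocardial infarction, new need for renal replacement therapy, severe bleeding, and non-elective cardiovascular surgery for device related complications". This list does not use the term re-intervention and sets no limit on when the surgery takes place.
- **Conversion to open mitral valve surgery during a transcatheter procedure:** two subclasses, "Secondary to mitral valve apparatus damage or dysfunction, requiring surgical valve repair or replacement, or" and "Secondary to procedural complications (such as cardiac perforation, removal of an embolized device, and so on". Neither MAE list refers to this entry by name.
- **Implant (index) procedure:** "The procedure in which placement of the investigational device in the mitral valve regurgitant orifice takes place".

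Protocol 10.1.2 has the CEC adjudicate by the definitions in the protocol and in its charter. Protocol 6.1 lists conversion to open valve surgery, emergency cardiac surgery, and device migration or embolization requiring intervention among the anticipated events.

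**The concern.** The component is meant to capture serious device complications that need a further intervention. Some of the most acute are dealt with while the patient is still on the table. If the adjudicator works from the Protocol 7.5 and SAP wording together with the re-intervention entry, a device-related conversion during the index procedure is not clearly an MAE. If the adjudicator works from the Section 17 MAE entry, it is. Both texts are in force and neither is said to take precedence.

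What is at stake is the headline safety result of a small single-arm study. With 60 patients and a purely descriptive analysis, one reclassified patient visibly changes the reported rate. The two lists also differ on death: Protocol 7.5 and the SAP count cardiovascular mortality, while the Section 17 entry says cardiac.

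**Working it through.** The plan states no figure for this point: there is no expected MAE rate, performance goal or conversion rate. The check is a side-by-side reading, followed by arithmetic for scale.

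**Step 1. Apply each definition to the same patient.** A is the Protocol 7.5 and SAP wording read with the re-intervention entry. B is the Section 17 MAE entry. Each event is taken to be device-related, with no other MAE component met.

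| Event | A | B |
|---|---|---|
| Open conversion during the index procedure | Not clearly an MAE | MAE |
| Surgical removal of an embolized device during the index procedure | Not clearly an MAE | MAE |
| Percutaneous retrieval during the index procedure | Not clearly an MAE | Not an MAE (not surgery) |
| Percutaneous repair or alteration of the implant after the procedure | MAE | Not an MAE (not surgery) |

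The first two rows are the conflict. The third is a gap under both. The fourth shows that neither list contains the other, so adopting one of them unchanged does not solve the problem.

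**Step 2. Why A leaves out the in-procedure events.** The re-intervention entry has three limits. The device must already be implanted. The act must be repair, alteration or replacement, or be directed at the access site. The intervention must follow the implant procedure. Conversion during the procedure fails the third limit on the natural reading. Retrieval also fails the second, because removal is not among the listed acts and Section 17 has a separate entry for explant. Timing is therefore not the only obstacle for retrieval.

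**Step 3. Is the patient in the denominator?** Yes. SAP Section 4 makes the PP population primary and admits ITT patients in whom the device was introduced into the body, absent major deviations. A converted patient with the device introduced stays in the analysis, and under A may count as MAE-free.

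**Step 4. Size.** SAP 6.3 uses Kaplan-Meier. With no censoring before day 30 this equals the crude proportion x/n, so crude proportions with Clopper-Pearson 95% intervals are used here. The event counts are assumed.

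- One patient: 1/60 = 1.7 points. At the first analysis, 1/30 = 3.3 points. In the pooled cohort of 60 + 50 = 110, 1/110 = 0.9 points.
- 4/60 = 6.7% (1.8 to 16.2). With one patient reclassified, 5/60 = 8.3% (2.8 to 18.4).
- Chance of at least one such event in 60 patients, 1 − (1 − p)^60, for an assumed p: 1% gives 45%, 2% gives 70%, 3% gives 84%, 5% gives 95%.

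These chances are for any such event. The net effect on the MAE rate is smaller, because patients who also have severe bleeding, stroke, MI, new renal replacement therapy or cardiovascular death are already counted. Severe bleeding starts at the MVARC major level, so many open conversions may enter by that route.

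**The case against.** The strongest reply is that the protocol does cover conversion. The Section 17 MAE entry includes non-elective cardiovascular surgery for device-related complications, without a time limit. That stands. A reader who looks only at the re-intervention entry might infer that no MAE component reaches an in-procedure conversion, and the documents do not support that. What remains is that Protocol 7.5 and the SAP, which govern the analysis, say something else.

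Second, the re-intervention entry can be read more generously. The post-procedure limit might attach only to the access site, and a device released minutes earlier might count as already implanted. This is a fair point about the grammar, but it leaves two adjudicators free to classify the same event differently.

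Third, these events are not hidden. An intervention before discharge fails procedural success, and therefore clinical success. SAP 6.6 also fails FDA Technical Success unless there was "No need for additional unplanned or emergency surgery or re-intervention related to the device or access procedure". This is correct, and it limits the harm. It does not correct the MAE rate, which is reported as the primary safety result in its own right.

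Fourth, the CEC charter may settle the matter. It is not among the documents, so this cannot be confirmed or excluded.

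**Conclusion.** The protocol defines the device-complication component of its primary safety endpoint in two incompatible ways. A device-related open conversion during the index procedure is an MAE under one and not clearly so under the other. In-procedure percutaneous retrieval is not clearly an MAE in itself under either. The definitions should be reconciled before events are adjudicated.

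The size is modest: 1.7 points per reclassified patient at n=60. The number of such patients is unknown, because the documents give no event rate; the 1% to 5% range is an assumption. No success criterion turns on the result, since the analysis is descriptive.

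Two stronger conclusions are tempting and should not be drawn. One is that the plan biases the 30-day MAE rate downward. That follows only if the Protocol 7.5 and SAP wording is applied with the restrictive reading of re-intervention, and only for patients with no other MAE. The other is that timing alone decides whether a rescue counts. For retrieval, the list of qualifying acts matters as well, so it is not clear that retrieval the next day would count either.

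**What to change.** Use one MAE definition throughout: the synopsis, Protocol 7.5, 7.6 and Section 17, and SAP 3.1, 3.2, 6.3 and 6.4. Settle cardiac versus cardiovascular mortality in the same edit.

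For the device-complication component, state that it counts unplanned surgery (including the conversions defined in Section 17) and unplanned percutaneous retrieval for study-device-related complications, from the start of the index procedure to day 30. Keep the post-procedure re-interventions that Protocol 7.5 already covers. The later MAE endpoints should use the same component over their own periods.

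Deleting the post-procedure limit from the re-intervention entry is not enough. The requirement that the device already be implanted and the three listed acts would remain, so retrieval would still be doubtful and the two MAE lists would still disagree.

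Repeat the agreed wording in the CEC charter. If events have already been adjudicated, review the in-procedure conversions and retrievals against the new text.

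The cost is a short amendment to the protocol, SAP and charter. Protocol Table 5 already collects adverse events and device disposition at the procedure, so little or no new data collection should be needed. The MAE rate may become slightly less favourable.
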